1. Any new disorder or disease that may affect the subject's participation in the study, or place the subject at increased risk, or for which epinephrine use is contraindicated.
2. Poor compliance in patch application (below 80%) during the previous year of participation in MILES.

**Primary
Endpoint:** The primary efficacy endpoint will be the percentage (%) of subjects who are treatment responders after the first 12 months of EPIT.

A treatment responder is defined as a subject who meets at least one of the following criteria:

- A ≥ 10 -fold increase in the Cumulative Reactive Dose (CRD) of cow's milk proteins at the Month 12 DBPCFC as compared to baseline value and reaching at least 144 mg of cow's milk proteins (approximately 4.5 mL of milk)
- A CRD of cow's milk proteins ≥ 144 mg (approximately 45 mL of milk) at the Month 12 DBPCFC.

Secondary Endpoints:**Secondary Efficacy Endpoints up to Month 12 (double-blind, placebo-controlled treatment period):**

- The mean and median CRD of cow's milk proteins at Month 12 and change from baseline.
- The change from baseline value in levels of sIgE and allergen-specific immunoglobulin G4 (sIgG4) to cow's milk at all timepoints evaluated up to Month 12.
- The change from baseline value in levels of sIgE and sIgG4 to caseins, α -lactalbumin, and β -lactoglobulin at all timepoints evaluated up to Month 12.
- The change from baseline in SPT wheal at all timepoints evaluated up to Month 12.
- The change in the severity of symptoms elicited during the milk DBPCFC from baseline to Month 12.
- The change from baseline in Quality of Life (QoL) assessments at Month 12.

Endpoints after Month 12 (open-label treatment periods with Viaskin Milk 500 μ g up to 48 months and Viaskin Milk 300 μ g for 24 months):

- The percentage (%) of subjects who are treatment responders over the course of open-label treatment with Viaskin Milk 500 μ g and 300 μ g.
- The CRD of cow's milk proteins over the course of open-label treatment with Viaskin Milk 500 μ g and 300 μ g.
- The levels of sIgE to cow's milk over the course of open-label treatment with Viaskin Milk 500 μ g and 300 μ g.
- The levels of sIgG4 to cow's milk proteins over the course of open-label treatment with Viaskin Milk 500 μ g.
- The levels of sIgE and sIgG4 to caseins, α -lactalbumin, and β -lactoglobulin over the course of open-label treatment with Viaskin Milk 500 μ g and 300 μ g.

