8.1.6.1 Primary Efficacy Endpoint and Analysis

The primary efficacy endpoint will be the percentage (%) of subjects who are treatment responders after 12 months of EPIT treatment.

A treatment responder is defined as a subject who meets at least one of the following criteria:

- A \geq 10-fold increase in the CRD of cow's milk proteins at the Month 12 DBPCFC as compared to baseline value and reaching at least 144 mg of cow's milk proteins (approximately 4.5 mL of milk).
- A CRD of cow's milk proteins \geq 1444 mg (approximately 45 mL of milk) at the Month 12 DBPCFC.

The CRD of cow's milk proteins is entered directly in CRF by the sites and is calculated as the sum of all doses of cow's milk proteins given during the challenge, including repeat doses if applicable, and exact quantity of the last dose given (if not given in totality).

The percentage of subjects who are treatment responders after 12 months of EPIT treatment will be calculated on the ITT population using missing = failure imputation method (ie, subjects with missing observation at Month 12 will be considered as non-responders).

The number and percentage of responders will be summarized overall and by age group, for each pooled dose level (Part A and Part B) and placebo group, for the blinded treatment period (Months 0 to 12).

Methods of exact logistic regression will be used to compare the proportion of treatment responders at Month 12 in each dose level to placebo, adjusting for age group, and including the treatment group as fixed effect, for subjects in the ITT population. P-values, odds ratios together with associated 95% Confidence Intervals (95% CI) will be presented.

The primary efficacy endpoint of this study, together with additional exploratory analyses, will assess the dose-response relationship and aim to inform the dose selection for phase 3. Model-based analytical approaches of exploratory dose finding (e.g., MCP-Mod) will be used to evaluate the dose-response relationship and estimate target dose(s).

Further details of the statistical methodology and considerations for the approaches to be used in the analysis will be specified in the SAP.

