8.2.1.2 OL-300 Analyses

Optional food challenge can be performed after 12 months and/or 24 months of open-label treatment with Viaskin Milk 300 μ g. No DBPCFC was performed at the end of 500 μ g period (prior to switch to open-label treatment with Viaskin Milk 300 μ g).

A responder in the OL-300 analyses is defined as a subject who meets at least one of the following criteria:

- A \geq 10-fold increase in the cow's milk proteins CRD at the Month 12 DBPCFC (VS3/VS4) [Month 24 (VS6/VS7)] after switch to Viaskin Milk 300 μ g as compared to baseline value and reaching at least 144 mg of cow's milk proteins
- A CRD of cow's milk proteins \geq 1444 mg at the Month 12 DBPCFC (VS3/VS4) [Month 24 DBPCFC (VS6/VS7)] after switch to Viaskin Milk 300 μ g

Two types of analyses will be performed, considering different timepoints as baseline:

1. Considering the CRD determined by screening DBPCFC as baseline CRD.
2. Considering the CRD determined by the DBPCFC which was conducted prior to the subject receiving any active treatment as baseline CRD. This refers to Month 12 DBPCFC for subjects randomized to the placebo treatment arm and to screening DBPCFC for subjects randomized to any active treatment arm.

This document is confidential

Statistical Analysis Plan

Both types of responders will be summarized overall and in each age-group, in total and by initial randomized treatment group (placebo/dose level/overall active) in the OLS-300.

For the calculation of rates and percentages, only the subjects with DBPCFC at the respective baseline and at Month 12 (VS3/VS4) [Month 24 (VS6/VS7)] after switch will be used.

8.2.2 Cumulative Reactive Dose (CRD) of Cow's Milk Proteins at Months 12 to 48

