8.2.2.2 OL-300 Analyses

Descriptive summaries will be presented overall and in each age-group, in total and by initial randomized treatment group (placebo/dose level/overall active) in the OLS-300, using different definitions of baseline values, as described in [Section 8.2.1.2](#)

1. Considering the CRD determined by screening DBPCFC as baseline CRD.
2. Considering the CRD determined by the DBPCFC which was conducted prior to the subject receiving any active treatment as baseline CRD.

The absolute CRD values at each timepoint will be presented, in addition with the change from screening and from last value prior any active treatment, taking the different types of baseline into account.

In addition the number (%) of subjects with CRD improvement / stable / deterioration from screening DBPCFC and from last DBPCFC prior any active treatment at each timepoint will be presented, using the following definitions:

- Improvement: CRD at timepoint > CRD at baseline
- Stable: CRD at timepoint = CRD at baseline
- Deterioration: CRD at timepoint > CRD at baseline

with baseline denoting screening DBPCFC or last DBPCFC prior any active treatment, respectively.

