16 APPENDICES

Listing Mock-ups and Table Mock-ups are separate documents.

This document is confidential

Statistical Analysis Plan

CCI

This document is confidential

SAP Version: 8.0
Controlled Document ID: CCI, Effective Date 29-Oct-2018
Filing requirements: TMF

Page 75 of 75

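### SAP 8.2.2.2 gives Deterioration the same inequality as Improvement, so as written improved subjects meet both classes and subjects whose CRD fell meet none

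*SAP*

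**What the plan says.** CRD over open-label treatment is a listed secondary endpoint (SAP 4.2.2). For the 300 µg period, SAP 8.2.2.2 states that "Descriptive summaries will be presented overall and in each age-group" and by randomised group. It adds a count and percentage of subjects in three classes at each timepoint, against two baselines:

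- Improvement is printed as "Improvement: CRD at timepoint > CRD at baseline".
- Stable is equality of the two CRDs.
- Deterioration is printed as "Deterioration: CRD at timepoint > CRD at baseline".

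The first baseline is the screening challenge. The second is the last challenge before any active treatment, which SAP 8.2.1.2 explains as "Month 12 DBPCFC for subjects randomized to the placebo treatment arm and to screening DBPCFC for subjects randomized to any active treatment arm".

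No other section of either document defines these classes. The shells cannot settle the matter, because SAP 16 says "Listing Mock-ups and Table Mock-ups are separate documents".

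On the secondary point, the second responder criterion reads "≥ 144 mg (approximately 45 mL of milk) at the Month 12 DBPCFC" in the protocol synopsis (Primary Endpoint) and "1444 mg (approximately 45 mL of milk) at the Month 12 DBPCFC" in protocol 8.1.6.1. SAP 4.1 and SAP 8.2.1.2 also carry 1444 mg.

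**The concern.** Improvement and Deterioration are opposite outcomes with one rule between them, and nothing covers a fall. The responder criteria in SAP 4.1 and 8.2.1.2 treat a higher CRD as benefit, so the printed Deterioration rule also points the wrong way.

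Among the planned CRD summaries, this table is the one that counts subjects who lost ground. Responder rates do not separate stable from worse, and a summary of mean or median change does not give the count. If the rule is programmed as printed, the unfavourable row is filled with subjects who improved, and those who worsened disappear. The error would recur overall, in each age group, in each randomised group, for both baselines and at each timepoint.

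**Working it through.** The documents give no figure for this table, so the check is one of logic: apply the three printed rules to every pair of baseline and follow-up CRD that the challenges allow.

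**Inputs**

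- Screening ladder (protocol 7.3.1.1.1): 1, 3, 10, 30, 100, 300 mg. Cumulative: 1, 4, 14, 44, 144, 444 mg (6 values).
- Ladder at Month 12 and later (protocol 7.3.1.1.2): the same doses, then 1000, 2000, 3000 mg. Cumulative: 1, 4, 14, 44, 144, 444, 1444, 3444, 6444 mg (9 values). These sums reproduce the 144 and 1444 mg of the responder criteria.
- Rules (SAP 8.2.2.2), with b the baseline and t the follow-up CRD: Improvement t > b; Stable t = b; Deterioration t > b.

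**Screening baseline, full doses, no repeats.** There are 6 × 9 = 54 pairs. The i-th lowest baseline has 9 − i higher follow-up values, so:

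- t > b: 8 + 7 + 6 + 5 + 4 + 3 = 33, each in both Improvement and Deterioration
- t = b: 6, Stable
- t < b: 0 + 1 + 2 + 3 + 4 + 5 = 15, in no class

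**Month 12 baseline** (second definition, placebo-randomised subjects). There are 9 × 9 = 81 pairs: (81 − 9)/2 = 36 double-classified, 9 Stable, 36 unclassified.

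**Allowing at most one repeated dose per challenge.** A challenge that stops at step k has k + 1 possible totals. That gives 2 + 3 + … + 7 = 27 distinct screening values and 2 + 3 + … + 10 = 54 distinct follow-up values. The 27 screening values are also the 27 lowest follow-up values. Of 27 × 54 = 1458 pairs, 27 are Stable, 0 + 1 + … + 26 = 351 fall and are unclassified, and 1458 − 27 − 351 = 1080 rise and are double-classified. Partial last doses are not enumerated.

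**With Deterioration as t < b**, every pair falls in exactly one class: 33 / 6 / 15 of 54 and 36 / 9 / 36 of 81.

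**Effect on the printed rows.** Let I, S and D be the true numbers of subjects whose CRD rose, was unchanged and fell. If each rule is programmed as a separate flag, the rows read I, S, I and sum to 2I + S. The number challenged is I + S + D, so the rows are out by I − D. For an assumed split of 100 subjects:

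| True rise / same / fall | Rows as printed | Sum | Without a class |
|---|---|---|---|
| 60 / 25 / 15 | 60 / 25 / 60 | 145 | 15 |
| 80 / 10 / 10 | 80 / 10 / 80 | 170 | 10 |
| 40 / 30 / 30 | 40 / 30 / 40 | 110 | 30 |

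The splits are illustrations only. The rows would sum correctly only by chance, when I = D.

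**Whom the second baseline concerns.** It differs from the first only for placebo-randomised subjects. In Part A these are 3 × 2 = 6. In Part B, 180 were randomised 1:1:1:1, so 180/4 = 45 is assumed. That makes about 51 of the 198 randomised, before attrition and before the challenge became optional.

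**Secondary point.** The synopsis equates 144 mg to 4.5 mL in its first bullet, that is 144/4.5 = 32 mg/mL. At 32 mg/mL, 45 mL is 1440 mg, which fits 1444 mg and not 144 mg. Read literally, the synopsis would make the ten-fold criterion redundant, since that one already requires 144 mg.

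**The case against.** The intended meaning is hardly in doubt: with > given to Improvement and equality to Stable, only < is left for a class named Deterioration. A programmer may well have used it, and the quality control in SAP 15 covers program logic and review of output. The Improvement and Stable rows are correctly defined, and the true Deterioration count can be recovered as the number with both challenges minus those two. Double-counting also depends on the coding: with an exclusive if/else-if, improved subjects would be counted once and the Deterioration row would be empty. The table is a descriptive, uncontrolled summary of optional challenges, so the matter could be called purely typographical. The pair counts say nothing about how many subjects are affected.

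Most of this stands, and it limits the size of the point. It does not remove it. Under either coding, subjects whose CRD fell have no class, and a check made against the SAP wording would confirm the wrong rule. This is current text that states an analysis rule for a listed secondary endpoint, not a slip in background prose.

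The synopsis slip could be a digit lost in reading the PDF, and its own 45 mL shows what was meant. That is why it is treated as minor.

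**Conclusion.** The concern holds: SAP 8.2.2.2 is wrong as written and should be fixed. The Deterioration row would hold the subjects who improved, or nobody, depending on the coding, and subjects whose CRD fell would be missing from the table.

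The consequence is small in inferential terms. No hypothesis test, power, Month 12 result or open-label responder rate is affected, and absolute CRDs and their changes appear alongside. For subjects randomised to active treatment both baselines are the screening challenge, so the table does not measure change within the open-label period in any case.

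The conclusion rests on the sign having been read correctly from the PDF; the neighbouring signs in the section read normally, and the source page would settle it. It makes no claim about outputs, because the mock-ups and programs are not in the documents.

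The synopsis threshold is an inconsistency only. The Month 12 analysis is complete and nothing shows that 144 mg was applied.

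**What to change.** In SAP 8.2.2.2, change the rule to: Deterioration: CRD at timepoint < CRD at baseline. Then:

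- Check the table mock-ups and programs against the corrected rule.
- Confirm that the three rows sum to the number of subjects with both challenges, and that the Deterioration count equals the number with a negative change in CRD. The second check matters because the rows can sum correctly by chance under the printed rule.
- SAP 2.2.1 plans separate Year 1 and final analyses of the 300 µg period, and the documents do not say whether Year 1 has been run. Apply the check to any Year 1 table already produced, and correct it if needed.

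The cost is one character in the SAP and a short programming check, with no effect on data or design.

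Secondary: confirm the synopsis figure against the source page and align it to 1444 mg. Protocol modifications go to the IRB (protocol 11.1), so this can wait for the next amendment.

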8.2.3 Immunological Markers

8.2.3.1 Double-blind Month 12 and OL-500 analyses

Repeated-measures ANCOVA models were built to compare the mean absolute change from baseline value (Visit 1) in

- 1) Cow's milk specific IgE
- 2) Cow's milk specific IgG4
- 3) Specific IgE to caseins
- 4) Specific IgG4 to caseins
- 5) Specific IgE to α -lactalbumin
- 6) Specific IgG4 to α -lactalbumin
- 7) Specific IgE to β -lactoglobulin
- 8) Specific IgG4 to β -lactoglobulin

using all time points evaluated up to Month 12 between each dose level group and placebo for subjects in the ITT.

Treatment group, treatment-by-time point interaction, age group, and baseline parameter value were included in the model. The distribution of each parameter was

This document is confidential

Statistical Analysis Plan

examined graphically (Bar-Chart) and a natural log transformation of the data was performed to be used in the analysis. The adjusted LS Mean and LS-Mean differences versus placebo and corresponding p-values at each time point (Week 3, Month 3, Month 6, and Month 12) were reported together with associated 95% CI. P-values for treatment effect all time points taken together were also provided. This ANCOVA model will not be repeated for open-label time points.

Actual values and changes from baseline for the immunological markers were summarized overall and for each age group, by (initial randomized) treatment group (dose level/placebo/overall active/total), at each time point until Month 12 for the randomized blinded treatment period.

Same summaries were provided for the Viaskin Milk 500 μ g open-label treatment period on the OLS-500. Change from Month 12 was also be tabulated for this period, if applicable. Similarly, the last value in the Viaskin Milk 500 μ g open-label treatment period was summarized.

Actual values and changes from baseline for the immunological markers will be displayed graphically by treatment group in the course of time.

8.2.3.2 OL-300 Analyses

During OL-300 analyses, Cow's milk specific IgG4 were no longer collected and analyzed.

The following values will be summarized for the immunological markers using descriptive statistics overall and for each age group, visit and time point in total and by initial randomized treatment group (placebo/dose level/overall active) on the OLS-300.

- Absolute values at Month 0, Month 12, last value prior to switch to Viaskin Milk 300 μ g and all scheduled visits in the analyzed OL-300 period
- Changes from last value prior to any active treatment
- Changes from last value prior to switch to Viaskin Milk 300 μ g

Actual values for the immunological markers will be displayed graphically by treatment group in the course of time during the analyzed OL-300 period.

8.2.4 Skin Prick Test

8.2.4.1 Double-blind Month 12 and OL-500 analyses

Actual values and change from baseline of SPT mean wheal diameter were summarized at all time points using descriptive statistics overall and for each age group, in total and by randomized treatment group (placebo/dose level/ overall active), on the ITT, for the randomized blinded treatment period. Same summaries were provided on the OLS-500, for the Viaskin Milk 500 μ g open-label treatment period, if applicable. Similarly, the last value in the Viaskin Milk 500 μ g open-label treatment period was summarized.

This document is confidential

Statistical Analysis Plan

The change in SPT average wheal diameter from baseline was also assessed by looking at the ratio of the average wheal diameter at each time point versus baseline categorized as:

- Significant improvement, if the ratio ≤ 0.75 ,
- No significant improvement, if the ratio > 0.75 .

The number and percentages of subjects with or without significant improvement was then compared between each dose level group and placebo at each respective visit up to Month 12 using the chi-square test or exact logistic regression (similar model as for the primary criteria) in case of low sample sizes (at least one theoretical frequency lower than 5).

The number of subjects with a mean wheal diameter equals to 0 was presented.

Repeated-measures ANCOVA model (same model as for Immunological Markers) was built to compare the change from baseline value in SPT average wheal diameter at all time points evaluated up to Month 12 between each dose level group and placebo for subjects in the ITT. The distribution of the SPT average wheal diameter was examined graphically (bar chart) and a \log_{10} -transformation of the data was performed to be used in the analysis. This ANCOVA model will not be repeated for open-label time points.

SPT results were also listed.

8.2.4.2 OL-300 Analyses

The following values will be summarized for the SPT using descriptive statistics overall and for each age group, visit and time point in total and by initial randomized treatment group (placebo/dose level/overall active) on the OLS-300.

- Absolute values at Month 0, Month 12, last value prior to switch to Viaskin Milk 300 μ g and all scheduled visits in the analyzed OL-300 period
- Changes from last value prior to any active treatment
- Changes from last value prior to switch to Viaskin Milk 300 μ g

The change in SPT average wheal diameter from both baselines will also be assessed by the ratio of the average wheal diameter at each time point versus baseline categorized as:

- Significant improvement, if the ratio ≤ 0.75 ,
- No significant improvement, if the ratio > 0.75 .

The number and percentages of subjects with or without significant improvement with respect to both baselines will be presented at each timepoint.

The number of subjects with a mean wheal diameter equal to 0 will be presented.

This document is confidential

Statistical Analysis Plan

8.2.5 Analysis of Severity during the Milk DBPCFC

8.2.5.1 Double-blind Month 12 and OL-500 analyses

The number of subjects with any objective and subjective allergic reaction during the different DBPCFC for both formulas was summarized overall and for each age group, in total and by (initial randomized) treatment group (placebo/dose level/overall active) for ITT, and OLS-500, respectively.

For the milk formulas only, the number of subjects with the specific objective and subjective allergic reaction during the different DBPCFC were summarized overall and for each age group, in total and by (initial randomized) treatment group (placebo/dose level/overall active) for ITT, and OLS-500, respectively.

The severity of symptoms elicited during the milk DBPCFC were assessed at Screening, Months 12, 24, 36 and 48. Grading of symptoms were done using the grading definition in the Oral Food Challenge (OFC) Symptom Score Sheets. Each symptom (objective and subjective) will be graded once per DBPCFC-Visit.

A total objective severity score was derived as the sum of the severity grades (0, 1, 2 or 3) of the following objective symptoms: pruritus, urticaria/angioedema, rash, sneezing/itching, nasal congestion, rhinorrhea, laryngeal, wheezing, diarrhea, vomiting, cardiovascular and conjunctivitis for DBPCFC with cow's milk formula.

A total subjective severity score was derived as the sum of the severity grades (0, 1, 2 or 3) of the following subjective symptoms: itchy mouth, itchy throat, nausea and abdominal pain for DBPCFC with cow's milk formula.

The total objective and subjective severity score was summarized (absolute and change from baseline) overall and for each age group, in total and by (initial randomized) treatment group (placebo/dose level/overall active), at Screening and Month 12 for subjects on the ITT in the randomized blinded treatment period.

Time-to-first objective symptom at Months 12, was summarized and Kaplan-Meier curves were provided for Month 12, overall and for each age group, in total and by randomized treatment-group (dose level/placebo/overall active). Patients without any objective symptom during the DBPCFC were censored at the time of discharge.

